4.3 Screen Failures

Screen failures are defined as patients who consent to participate in the clinical study but who do not meet 1 or more criterion required for participation and are not subsequently randomized to treatment in the study. A minimal set of screen failure information is required to ensure transparent reporting of screen failure patients, to meet the Consolidated Standards of Reporting Trials publishing requirements, and to respond to

queries from regulatory authorities. Minimal information includes demography, screen failure details, eligibility criteria, and any SAE(s).

Individuals who are screen failures due to out of range laboratory values can be retested once during the 28-day screening period. If the repeated lab values remain exclusionary, the subject will be considered a screen failure. Redrawing samples if previous samples were unable to be analyzed would not count as a retest since the previous result was never obtained.

Patients that screen fail for the study may be re-screened at a later date (i.e., after the 28-day screening window has expired) following re-consent. A new patient ID must be assigned in this instance.

4.4 Premature Discontinuation

4.4.1 Premature Discontinuation of Investigational Product

Patients should discontinue the study medication if any of the following occurs:

- Confirmed, active infection with the severe acute respiratory syndrome coronavirus 2 (SARS-CoV-2) virus
- Serious infection
- Invasive fungal infection
- Malignancy (except for non-melanoma skin cancer)
- Hepatitis B virus reactivation
- Demyelinating disease
- Heart failure
- Lupus-like syndrome
- Hypersensitivity reaction
- Gastrointestinal perforation
- WBC count: $<1 \times 10^3/\mu\text{L}$
- ANC: $<0.5 \times 10^3/\mu\text{L}$
- Lymphocyte count: $<0.3 \times 10^3/\mu\text{L}$
- Platelet count: $<50 \times 10^3/\mu\text{L}$
- Hemoglobin: $<6.5 \text{ g/dL}$

- AST or ALT:
 - $>5\times\text{ULN}$ persisting for 2-weeks after study medication interruption or second occurrence of $>5\times\text{ULN}$
 - $>3\times\text{ULN}$ and (total bilirubin $>2\times\text{ULN}$ or international normalized ratio [INR] >1.5)
 - $>3\times\text{ULN}$ with appearance of fatigue, nausea, vomiting, right upper quadrant pain or tenderness, fever, rash and/or eosinophilia ($>5\%$)
- Serum creatinine: $>2\times\text{ULN}$ persisting for 2-weeks after study medication interruption or second occurrence of $>2\times\text{ULN}$
- The patient withdraws his/her consent to participate in the study.
- The patient develops an illness that would interfere with his/her continued participation in the study.
- The patient is noncompliant with study procedures or medication, in the opinion of the investigator.
- The patient is confirmed to be pregnant.
- The sponsor or regulatory agency requests withdrawal of the patient.

The investigator will make every effort to ensure that patients who prematurely discontinue study medication complete the Day 84, end of study assessments.

Patients who discontinue study medication prematurely may be replaced at discretion of the sponsor.

4.4.2 Premature Discontinuation from the Study

Participation in the study is strictly voluntary. A patient has the right to withdraw from the study at any time for any reason, without any reprisal.

The investigator has the right to terminate participation of a patient for any of the following reasons:

- Difficulties in obtaining blood samples
- Violation of the protocol
- Severe AEs or SAEs
- Any other reason relating to the patient's safety or integrity of the study data

If a patient is withdrawn from the study, the study monitor/sponsor will be informed immediately. If there is a medical reason for withdrawal, the patient will remain under the supervision of the investigator until satisfactory health has returned.

If the patient withdraws consent for disclosure of further information, the sponsor may retain and continue to use any collected data before such a withdrawal of consent. If a patient withdraws from the study, he/she may request destruction of any samples taken and not tested, and the investigator must document this in the site study records.

Although a patient is not obliged to give his/her reason(s) for withdrawing prematurely from a study, the investigator should make a reasonable effort to ascertain the reason(s), while fully respecting the patient's rights.

At the time of premature study discontinuation, the investigator should make every effort to ensure the patient completes the assessments indicated at the end of study (Week 12) visit; see [Table 1](#).

Patients who prematurely discontinue from the study cannot subsequently rejoin the study. For details on the discontinuation of study sites or the study as a whole, see [Section 14](#).

4.4.3 *Lost to Follow-up*

A patient will be considered lost to follow-up if he/she repeatedly fails to return for scheduled visits and is unable to be contacted by the study site.

The following actions must be taken if a patient fails to return to the clinic for a required study visit:

- The site must attempt to contact the patient and reschedule the missed visit as soon as possible, counsel the patient on the importance of maintaining the assigned visit schedule, and ascertain whether or not the patient wishes to and/or should continue in the study.
- Before a patient is deemed lost to follow-up, the investigator (or designee) must make every effort to regain contact with the patient (where possible, 2 telephone calls and, if necessary, a certified letter to the patient's last known mailing address or local equivalent methods). These contact attempts should be documented in the patient's research record.
- Should the patient continue to be unreachable, he/she will be considered to have withdrawn from the study.

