to the patient providing informed consent, or routine clinical procedures that are not the result of an AE (e.g., elective surgery for a pre-existing condition that has not worsened) need not be considered AEs or SAEs. If anything untoward is reported during the procedure, that occurrence must be reported as an AE or SAE as per the definitions.

In general, hospitalization signifies that the patient has been detained (usually involving at least an overnight stay) at the hospital or emergency ward for observation and/or treatment that would not have been appropriate in the physician's office or outpatient setting. When in doubt as to whether hospitalization occurred or was necessary, the AE should be considered serious.

Disability/incapacity: an AE is incapacitating or disabling if the experience results in a substantial and/or permanent disruption of the patient's ability to carry out normal life functions.

7.1.3 *Clinical Laboratory Abnormalities and Other Abnormal Assessments*

Laboratory abnormalities without clinical significance should not be recorded as AEs or SAEs. However, laboratory abnormalities (e.g., clinical chemistry, hematology, coagulation, lipids, and urinalysis abnormalities) that require medical or surgical intervention or lead to study medication interruption, modification, or discontinuation must be recorded as an AE or SAE, as applicable. In addition, laboratory or other abnormal assessments (e.g., in ECGs, X-rays, or vital signs) that are associated with signs and/or symptoms must be recorded as an AE or SAE if they meet the definition of an AE or SAE as described in [Sections 7.1.1](#) and [7.1.2](#). If the underlying cause for the laboratory abnormality is known, record the etiology or diagnosis (e.g., anemia), rather than the laboratory result (i.e., decreased hemoglobin).

For specific information on handling of clinical laboratory abnormalities, see [Section 5.3.2](#).

7.2 *Assessment of Adverse Events*

7.2.1 *Severity*

The investigator will determine the intensity of the AE according to the definitions below:

- **Mild:** An event that is easily tolerated by the participant, causing minimal discomfort and not interfering with everyday activities
- **Moderate:** An event that causes sufficient discomfort and interferes with normal everyday activities
- **Severe:** An event that prevents normal everyday activities. An AE that is assessed as severe should not be confused with a SAE. Severe is a category utilized for

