7.5 Adverse Event and Serious Adverse Event Follow-up

During the study (and after the end of study visit), all AEs and SAEs should be followed proactively by the investigator until the event resolves or the condition stabilizes to a level acceptable to the investigator, until the event is otherwise explained, or until the patient is lost to follow-up. At the time the patient's study participation ends, all ongoing AEs and SAEs should be evaluated for resolution. New or updated information will be recorded in the originally completed eCRF and the investigator will submit any updated SAE information to the sponsor within 24 hours of receipt of the information.

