11.2 Protocol Adherence and Deviations

The investigator and site personnel should conduct the study in compliance with the protocol and should use continuous vigilance to identify and report protocol deviations.

A protocol deviation is any change, divergence, or departure from the study design or procedures defined in the protocol that may be on the part of the investigator, site personnel, or the patient.

Important protocol deviations are a subset of protocol deviations that may significantly impact the completeness, accuracy, and/or reliability of the study data or that may significantly affect a patient's rights, safety, or well-being. For example, important protocol deviations may include enrolling patients in violation of key eligibility criteria designed to ensure a specific patient population or failing to collect data necessary to interpret primary endpoints, as this may compromise the scientific value of the study.

The investigator should not implement any deviation from the protocol without agreement from the sponsor and prior review and approval from the IRB/IEC of an amendment, except where necessary to eliminate an immediate hazard to a study patient, or when the change involves only logistical or administrative aspects of the study, such as a change in a monitor or telephone number.

In the event of an important protocol deviation, the investigator will discuss the deviation with the sponsor's medical monitor and will come to an agreement as to whether the patient should be withdrawn from the study due to the important protocol deviation.

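### Investigators may end participation for any severe AE or SAE, and the readable Per-Protocol definition admits off-drug hsCRP values; a retention sentence and an analysis flag would close both gaps

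*Combined protocol and SAP*

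**What the plan says.** Section 4.4.1 lists events after which a patient should come off study medication, among them serious infection, heart failure and defined liver, renal and blood-count limits. The site is then to do what it can so that "patients who prematurely discontinue study medication complete the Day 84, end of study assessments".

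Section 4.4.2 deals with leaving the study. It reads "The investigator has the right to terminate participation of a patient for any of the following reasons", and one of the four grounds is "Severe AEs or SAEs". When a patient leaves, the investigator is to try to "ensure the patient completes the assessments indicated at the end of study (Week 12) visit", and the text ties this to the time of exit. The step is final: "Patients who prematurely discontinue from the study cannot subsequently rejoin the study".

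Section 7.2.1 rates severity by effect on daily life and keeps it apart from seriousness: "An event that prevents normal everyday activities. An AE that is assessed as severe should not be confused with a SAE".

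Section 11.2 attaches a decision step to a neighbouring ground. After an important protocol deviation, the sponsor's medical monitor is brought in by the investigator, and the two "will come to an agreement as to whether the patient should be withdrawn from the study due to the important protocol deviation".

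Section 7.5 protects follow-up of events that have already occurred: "all AEs and SAEs should be followed proactively by the investigator until the event resolves".

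The Protocol Summary (Analysis Populations, Efficacy Analyses) defines the Per-Protocol population by two conditions: a completed Day 84 visit, and valid hsCRP at 6 or more of 7 scheduled times. Whether the hsCRP effect is sustained is judged from the median percent change in that population.

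**The concern.** The two sections overlap for events such as serious infection, and 4.4.2 reaches further. A severe but non-serious event that is not on the 4.4.1 list can end participation for good. Safety is the primary objective, with laboratory, vital sign and ECG changes among its endpoints. If harm is itself a ground for exit, scheduled data stop for a reason related to the outcome, and whether they stop depends on each investigator's choice.

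The second issue runs the other way. Section 4.4.1 rightly brings patients back on Day 84 after they stop drug, but the readable Per-Protocol definition does not ask whether they were still taking it. Section 1.2 sets the trial's main pharmacodynamic question: earlier p38 inhibitors showed an early fall in CRP and a return to baseline within 4 to 8 weeks, and the trial asks whether ATI-450 avoids this. A rebound after stopping drug could look like the same pattern and count against ATI-450.

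**Working it through.** The plan states no figure on this point, so the sections are set side by side and the visits counted.

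**Inputs.** Treatment-period visits are Days 7, 14, 28, 42, 56 and 84 (Section 3.1). Visit 9 is 30 to 37 days after the last dose. 25 patients are planned, 15 evaluable, randomised 3:1. The documents give no expected number of severe AEs or exits.

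**Step 1: visits after an event with last dose on Day 28.** Three treatment-period visits remain: Days 42, 56 and 84.
- Section 4.4.1 as written names 1 of 3 (Day 84).
- Section 4.4.2 secures 0 of 3 on schedule. The Week 12 set is done 84 − 28 = 56 days early (84 − 42 = 42 for a Day 42 exit, 84 − 56 = 28 for Day 56).
- So one visit is lost through 4.4.2. The other two are unsecured because 4.4.1 names only Day 84.
- Visit 9 falls on Day 28 + 30 = 58 to 28 + 37 = 65. No readable text cancels it, and Table 1 schedules laboratory tests, vital signs, ECG and hsCRP there.
- If AE collection stops at Visit 9, capture of new AEs ends 84 − 65 = 19 to 84 − 58 = 26 days before Day 84. This is conditional on that reading of Section 7.3.

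**Step 2: weight of one patient.** Assuming exact 3:1, 25 × 0.75 = 18.75, about 19 and 6. One patient is 1/19 = 5.3% or 1/6 = 16.7%. Among 15 completers, 15 × 0.75 = 11.25, about 11 and 4, so 1/11 = 9.1% or 1/4 = 25%.

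**Step 3: Per-Protocol count.** The 7 times are taken as Days 1, 7, 14, 28, 42, 56 and 84, and the value on the stop day counts as on drug.

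| Last dose | Only Day 84 kept (4.4.1 as written) | All visits kept, no flag | All visits kept, on-drug values counted |
|---|---|---|---|
| Day 28 | 4 + 1 = 5, fails | 4 + 3 = 7, qualifies, 3 off drug | 4, fails |
| Day 42 | 5 + 1 = 6, qualifies, Day 84 value 42 days off drug | 5 + 2 = 7, qualifies, 2 off drug | 5, fails |
| Day 56 | 6 + 1 = 7, qualifies, Day 84 value 28 days off drug | 6 + 1 = 7, qualifies, 1 off drug | 6, qualifies, Day 84 value left out |

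If the 7 times were instead the six treatment visits plus Visit 9, a Day 42 stop gives 4 + Visit 9 + Day 84 = 6 and still qualifies.

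The second and third columns show why retention and the flag belong together: keeping more visits without a flag would also admit the Day 28 stop.

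**The case against.** The strongest objection is that the protocol already has an order of routes. Section 4.4.1 is directive and 4.4.2 is only a right. For a positive baseline SARS-CoV-2 test (5.1.5) and pregnancy (5.3.3) the route is set, and after a possible Hy's Law event Appendix 1 allows the participant to continue in the study. This stands. A reader might infer that the sections contradict each other or leave no default; the documents do not support that. What remains is narrower: the right covers severe events outside the list, and Appendix 1 gives permission for one kind of event, not a general rule.

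Safeguards also stand. Section 4.4.2 requires the sponsor to be told at once and keeps a medically withdrawn patient under the investigator's care until recovery. Section 7.4 needs investigator and sponsor monitors to agree that an SAE is satisfactorily resolved. Event follow-up, the 30-day AE window, Visit 9, and Safety and ITT membership all survive exit. The contrast with 11.2 is limited too, since that step covers important deviations only.

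A reader might also infer that Day 84 summaries omit patients who left because of harm. That is not shown. Week 12 assessments done at exit might be tabulated at Week 12 or elsewhere. The detailed SAP to which the protocol refers is not in the readable text, and part of Section 8.4 is redacted. The headings of 6.3 and 6.6 and much of 6.7 are also blacked out and could hold related rules.

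Finally, the Per-Protocol issue is separate from 4.4.2 and depends on how a valid hsCRP value is defined. Both points are fair, and the conclusion is worded accordingly.

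**Conclusion.** The point holds as a low-cost improvement, not as a contradiction in the protocol.

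First, 4.4.2 lets each investigator end participation for any severe AE or SAE, with no agreement step in the readable text. For an event on Day 28, this costs the one on-schedule visit that 4.4.1 would have secured. How many patients this would affect cannot be derived from the documents.

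Second, the readable Per-Protocol definition admits a patient off drug since Day 42. In an ATI-450 arm of about 11 completers that is 9% of the set. Because the summary is a median, one such value can move it by at most one place in the ordered values, so the effect is bounded but falls on the trial's key pharmacodynamic question. This rests on the 7 times being as assumed and on no unseen definition of valid that excludes off-drug values.

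No claim is made about missing-data handling or visit mapping.

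**What to change.** 1. State in 4.4.1 and 4.4.2 that patients who stop study medication for an AE, including a severe AE or SAE, are asked to stay for the remaining scheduled safety and hsCRP visits through Day 84, plus Visit 9. The exceptions are withdrawn consent, lost contact, or attendance that the investigator judges unsafe. Keep the investigator's safety discretion, and leave the pregnancy, baseline SARS-CoV-2 and Appendix 1 routes as they are.
2. Flag hsCRP values taken after permanent discontinuation of study medication. Keep them in the ITT summary, exclude them from the Per-Protocol sustained-effect summary, and count only unflagged values toward the 6 of 7. Name the 7 times. The same flag could be used to show laboratory, vital sign and ECG means with and without off-drug values.

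The cost is a few sentences of protocol wording, one derived flag, some visit burden for patients off drug, and a possibly smaller Per-Protocol set, since a Day 42 stop would no longer qualify. The visits are already in the schedule.

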5 DESCRIPTION OF STUDY ASSESSMENTS

Refer to [Table 1](#) for the Schedule of Assessments.

5.1 Demographics and Other Screening Assessments

Screening assessments that are also part of the safety assessments are described in [Section 5.3](#).

5.1.1 *Medical History*

Relevant medical history and current medical condition, including RA disease phenotype and duration as well as date of first diagnosis and previous treatments including any previous biologic or non-biologic therapy for RA will be recorded in the electronic case report form (eCRF).

At the baseline visit, inclusion/exclusion criteria will be reviewed and updated to ensure the patient remains qualified for the study. Significant findings that are observed after the patient has signed the ICF and prior to the first dose of study medication will be recorded as medical history on the eCRF. Any event observed after the patient has signed the ICF that meets the definition of a SAE will be recorded on the SAE eCRF.

5.1.2 *Demographics*

Demographic data, including year of birth/age, sex (at birth), and race, will be recorded in the eCRF.

5.1.3 *Tuberculosis Test*

An interferon-gamma release assay/QuantiFERON TB Gold test for active/latent TB will be performed at screening with analysis conducted by the sponsor's designated central laboratory. Patients with a negative test result will be eligible for the study.

In case of indeterminate results, the test may be repeated once. The patient can be included in the study if the repeat test is negative; however, if the repeat test is positive or indeterminate, the patient will be excluded from the study.

5.1.4 *Screening Clinical Laboratory Assessments*

Blood samples will be collected for clinical chemistry, coagulation, hematology, hsCRP, lipids, FSH, hepatitis B surface antigen, hepatitis B core antibody, hepatitis C antibody, and HIV-1/HIV-2. A serum pregnancy test will be performed on women of childbearing potential. All laboratory analyses will be performed by the sponsor's designated central laboratory.

5.1.5 COVID-19 Monitoring

At Baseline Visit 2, all patients entering the treatment phase of the study must have a nasopharyngeal (preferred) or oropharyngeal swab collected prior to the first dose of study medication to test for the presence of the SARS-CoV-2 virus. The sample will be sent to the study's central lab for analysis by reverse transcription polymerase chain reaction (RT-PCR) with results reported as either 'Detected' or 'Not detected' for SARS-CoV-2 viral particles. If central laboratory testing cannot be performed at the time of Baseline Visit 2 (i.e., lab supplies are not yet available) and the study site is able to perform equivalent testing locally, they may choose to do so, as long as the test results are available in the patient's research chart for sponsor review. Patients should not initiate study medication treatment in the absence of central laboratory or locally equivalent testing being performed.

Patients are allowed to dose with study medication in the interval between sample collection at Baseline Visit 2 and result reporting as long as there is no clinical suspicion of COVID-19 infection or recent exposure of the patient to an individual with a confirmed, active infection.

If the patient's results are positive for SARS-CoV-2 following sample collection at Visit 2, the patient will need to be notified immediately upon receipt of the results and treatment with study medication will be permanently discontinued. The patient should be advised to begin self-isolation and self-monitoring procedures according to any applicable local, state, and/or federal health recommendations. Referral to an appropriate health care provider for management of the patient's COVID-19 diagnosis should also be made. The patient should be seen for the post-treatment follow-up Visit 9 (see [Table 1](#)) only at such time that the investigator assesses the risk for incidental transmission from viral shedding to be minimized. The patient's COVID-19 diagnosis will be reported as medical history unless the patient's clinical course progresses such that criterion for SAEs reporting is met (See [Section 7.1.2](#)), in which case, all applicable safety reporting procedures will be followed by the site.

Sites will also have the option to perform an unscheduled test for the SARS-CoV-2 virus at any time during the treatment phase of the study should a patient's clinical presentation necessitate it in the investigator's opinion. The same notification and referral procedures, as outlined in the preceding paragraphs, should be followed by the site. However, it is expected that any COVID-19 diagnosis made from a sample collected after the initiation of study be reported as an AE per the requirements of [Section 7](#) of this protocol.

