7.3 Documenting and Reporting Adverse Events

Reporting of SAEs will begin when the patient has provided informed consent and will continue up to the end of study visit or 30 days after the last study drug administration whichever is later. Reporting of AEs will begin when the patient receives the first dose of study medication and will continue up to the end of study visit or 30 days after the last study drug administration, whichever is later. Any clinical AE that occurs between the time of consent and dosing Day 1 will be recorded as medical history.

Occurrence of AEs may be volunteered spontaneously by the patient; discovered as a result of general, nonleading verbal questioning by the study staff; or determined by physical examination or other safety assessments. All AEs will be monitored and recorded in the CRF throughout the entire study.

For all AEs, the investigator must pursue and obtain adequate information (a description of the event, severity, time of occurrence [including whether the AE onset was before, during, or after the study medication administration if the AE started on a dosing day], duration, and any action, e.g., treatment/follow-up tests). The outcome of the event should be provided along with the investigator’s assessment of the relationship to the

study medication. The investigator must also assess whether the event meets the criteria for classification as an SAE.

It is the investigator's responsibility to review all documentation (e.g., hospital notes, laboratory reports, and diagnostic reports) related to an AE. Wherever possible, the investigator's diagnosis, not the individual signs and symptoms, will be documented as the AE.

Investigators are not obligated to actively seek AEs or SAEs after the patient's conclusion of study participation. However, if the investigator learns of any SAE, including death, at any time after a patient has been discharged from the study, and he/she considers the event to be reasonably related to the study medication or study participation, the investigator must promptly notify the sponsor.

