8.4.2 Safety Analyses

The Safety population will be used for the analysis of safety data (AEs, exposure to study medication, clinical laboratory, vital signs, and ECG).

AEs will be coded with the MedDRA. Treatment-emergent adverse events (TEAEs) are defined as AEs with an onset date on or after the date of first administration of study medication and through the completion of the last follow up visit or before the date of last administration of study medication + 30 days (whichever is later). TEAEs will be presented by system organ class and preferred term in frequency tables. Patients with multiple AEs will be counted only once within each preferred term and system organ class. Key patient information for patients with an AE with an outcome of death, patients with SAEs, and patients with an AE leading to discontinuation of study medication will be listed.

Laboratory data (hematology, serum chemistry, coagulation, lipids, and urinalysis) will be converted to Système International units for reporting and processing purposes. Absolute values and changes from baseline will be presented descriptively. Laboratory data outside study-specific reference ranges will be listed.

Vital signs and ECG parameters will be presented descriptively.

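### After a positive pre-dose Visit 2 swab, a non-serious COVID-19 illness that starts after the first dose is sent to medical history and can drop out of the primary AE counts

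*Combined protocol and SAP*

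**What the plan says.** Under Section 5.1.5, every patient entering treatment has at Visit 2 a "swab collected prior to the first dose of study medication to test for the presence of the SARS-CoV-2 virus". The first dose need not wait for the answer: "Patients are allowed to dose with study medication in the interval between sample collection at Baseline Visit 2 and result reporting". A condition is attached: this may be done only "as long as there is no clinical suspicion of COVID-19 infection" and there has been no recent contact with a confirmed case. If the result is positive, "treatment with study medication will be permanently discontinued". This matches Section 4.4.1, which lists "Confirmed, active infection with the severe acute respiratory syndrome coronavirus 2 (SARS-CoV-2) virus" among the reasons for stopping. The COVID-19 "diagnosis will be reported as medical history unless the" course progresses far enough to meet the SAE criteria. The last paragraph of Section 5.1.5 treats a diagnosis from a sample taken once the study is under way as an AE under Section 7.

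The general rules use a different dividing line. Section 7.3 says "Reporting of AEs will begin when the patient receives the first dose of study medication" and reserves medical history for clinical events between consent and Day 1 dosing. Section 5.1.1 draws the same line at the first dose. Section 8.4.2 defines treatment-emergent events as "AEs with an onset date on or after the date of first administration of study medication", up to the end of follow-up.

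**The concern.** The special rule in Section 5.1.5 sorts events by when the swab was taken. Sections 7.3 and 8.4.2 sort them by when the event began. The two disagree for a patient dosed with the swab pending who then becomes ill without meeting SAE criteria. A site following the specific instruction would enter the diagnosis as medical history.

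Counts and percentages of AEs are part of the primary endpoint, so this affects the main output of the study. The patient has been dosed and stays in the Safety population, while the illness leaves the numerator. Severity grading, causality assessment and follow-up attach to AEs, so that information could be lost too. The background section describes a drug acting on a pathway that drives TNF-α, IL-1 and IL-6, so the course of an infection after exposure is relevant safety information.

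**Working it through.** The plan gives no figure on this point to reproduce, and the sample size rests on feasibility. The check is a comparison of rules, followed by arithmetic for scale.

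**Tracing one patient.** Take a patient with no suspicion of COVID-19 who is swabbed and dosed on Day 1, has a positive result, and develops non-serious symptoms on Day 3.

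1. Dosing is permitted by Section 5.1.5. Because suspected cases may not be dosed on a pending result, overt illness in such a patient would normally appear after the dose.
2. Section 5.1.5 sends the diagnosis to medical history. It foresees clinical progression but makes an exception only for SAEs.
3. Section 7.3: onset is after the first dose, so the illness is an AE and does not fit the medical-history window.
4. Section 8.4.2: onset is on or after the first-dose date, so the AE is treatment-emergent.
5. Section 7.3 also asks for the diagnosis, where possible, in place of individual symptoms as the AE term. With the diagnosis already in medical history, a site has little reason to enter the symptoms separately.
6. Section 7.2.1 separates severe from serious. An illness that prevents everyday activities, but is not serious, would still be medical history under step 2.
7. Had the same illness been diagnosed from a later sample, Section 5.1.5 would make it an AE.
8. The tables and the listing of AEs leading to discontinuation in Section 8.4.2 use events recorded as AEs. The Safety population in the Protocol Summary includes anyone with one dose.

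**Size of one omitted case.** Inputs: about 25 patients and 3:1 allocation (Section 3.1). 25 × 3/4 = 18.75 and 25 × 1/4 = 6.25, so about 19 and 6.

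- Active: 1/19 = 5.3 percentage points (1/18 = 5.6 if the split is 18:7).
- Placebo: 1/6 = 16.7 points (1/7 = 14.3 if the split is 18:7).
- Overall: 1/25 = 4 points.

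These apply to the percentage of patients with any AE only if that patient has no other AE.

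**Chance of a positive Visit 2 swab.** The positivity rate p is assumed. P(at least one in 25) = 1 − (1 − p)^25.

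- p = 1%: 1 − 0.99^25 = 1 − 0.778 = 22%; expected 25 × 0.01 = 0.25 patients.
- p = 2%: 1 − 0.98^25 = 1 − 0.603 = 40%; expected 0.5.
- p = 5%: 1 − 0.95^25 = 1 − 0.277 = 72%; expected 1.25.

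**From positive swab to omitted illness.** The patient must also be dosed before the result, become ill or worsen after dosing, and stay non-serious. As an illustration, suppose p = 2%, half of the positives become symptomatic after dosing, and the other conditions always hold. The rate is then 0.02 × 0.5 = 1%, and the chance is 1 − 0.99^25 = 22%, against 40% for a positive swab alone.

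**The case against.** The best defence is that the split by sample timing looks deliberate. The swab precedes the first dose, so a positive result shows an infection already present, and Sections 5.1.1 and 7.3 send pre-dose findings to medical history. This stands for the positive swab itself and for a patient who never has symptoms. It does not settle the classification of illness that begins or worsens later.

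A second defence is that Section 5.1.5 speaks of the diagnosis and does not exempt later symptoms from Section 7. Section 7.1.1 defines an AE broadly, Section 5.3.6 asks for new or worsening abnormalities to be reported, and AEs are collected at Visit 9, which these patients are told to attend. Section 7.1.3 requires an AE entry for laboratory abnormalities that lead to discontinuation. How a site would act is indeed a prediction. But Section 5.3.6 concerns physical examination and is qualified by appropriateness, Section 7.1.3 does not mention a PCR result, and Section 7.3 prefers the diagnosis to the symptoms. No text states which rule prevails.

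Three stronger readings are tempting, and the documents do not support them.

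- A reader might infer that any non-serious COVID-19 after Day 1 escapes the AE tables. It does not: a diagnosis from a later sample is an AE, and serious cases are captured either way.
- A reader might take 22% to 72% as the chance of a missing AE. It is the chance of a positive swab. Section 4.2 excludes known exposure during screening, and dosing on a pending result requires no suspicion, so high positivity is less plausible.
- A reader might infer that recording post-dose illness as an AE closes every gap in the discontinuation listing. It does not, because the positive result itself triggers withdrawal, so an asymptomatic patient still leaves with no AE attached.

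Stop dates are recorded in the eCRF (Section 6.10). Parts of Section 8.4 are blacked out and the eCRF guidance is not available, so how discontinuations are tabulated elsewhere cannot be judged.

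**Conclusion.** The inconsistency is real but narrow. It concerns a patient dosed on Day 1 with the Visit 2 swab pending, a positive result, and a non-serious illness with onset or worsening after the dose. For that patient Section 5.1.5 conflicts with Sections 7.3 and 8.4.2, and an event that belongs in the primary AE counts can be left out.

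At most one or two patients are likely to be affected, and quite possibly none. Because the arms are small, even one would show, above all on placebo. The scale figures rest on about 25 dosed patients, a split near 19:6, no other AE in the affected patient, and an assumed positivity of 1% to 5%. That the illness is omitted is an inference from the recording rules, though a direct one. Severity: minor.

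**What to change.** Reconcile Sections 5.1.5, 7.1.3, 7.3 and 8.4.2 on how these cases are recorded.

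- In Section 5.1.5, limit the medical-history entry to the positive pre-dose swab, including a positive that stays asymptomatic.
- Add one sentence: COVID-19 symptoms, or worsening, with onset after the first dose are recorded as an AE under Section 7.3 whatever their seriousness, with the action taken on study medication.
- In the paragraph on later samples, make clear that it means samples taken after the first dose of study medication. Its present wording refers to the start of the study and, read literally, could cover the Visit 2 swab.
- In Section 8.4.2, list discontinuations triggered by a positive Visit 2 swab alone, since they carry no AE. Say whether Section 7.1.3 is meant to apply to a PCR result.

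These changes concern recording and listing only and leave the dosing and stopping rules as they are. The cost is a few sentences, matching eCRF guidance and one listing. The downside is possibly one more non-serious AE in the tables.
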